6.5.3. Post-Treatment Period

Subjects should be followed until the later of either 30 days after the last dose of study treatment or until resolution/stabilization of any ongoing drug-related AEs and/or SAEs. For subjects with events that require follow-up, information regarding concomitant medications should be collected. Any necessary follow-up may be obtained in person or by telephone contact.

Subjects who have discontinued study treatment for reasons other than PD will be assessed per Revised Response Criteria for NHL or Guidelines for the diagnosis and treatment of CLL at a minimum of every 12 weeks until documentation of PD, start of new anti-cancer therapy or for up to 1 year from the last enrolled subject's first treatment (Cycle 1 Day 1) whichever comes first.

Long-term follow-up survival information will be obtained in all surviving subjects who permanently discontinue study therapy. Such information may be collected at ~3- to 6-month intervals at the sponsor's discretion through 3 years. This long-term follow-up information will be gathered during routine clinic visits, other study site contact with the subjects, or via telephone or e-mail with the subjects/caregivers or referring physician offices.

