Unless they withdraw consent for further follow-up, subjects who discontinue study therapy will continue on study for acquisition of safety information through \geq 30 days after the last dose of study treatment, and for further collection of long-term information regarding survival.

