14.9. Efficacy Analysis

The tumor response will be assessed by the modified criteria for NHL (Cheson 2014) and revised guidelines for the diagnosis and treatment of CLL (Hallek 2008, Cheson 2012) (see Appendix 2).

The objective response rate will be estimated for each dose escalation cohort and each expanded cohort. The estimate of the objective response rate will be calculated based on the maximum likelihood estimator (i.e., crude proportion of subjects whose best overall response is CR or partial remission [PR]). The estimate of the objective response rate will be accompanied by 2-sided 95% exact binomial confidence intervals.

The duration of objective response will be calculated for subjects who achieve CR or PR. For such subjects, the duration of objective response is defined as the number of days from the start date of PR or CR (whichever response is achieved first) to the first date that progressive disease is objectively documented. The duration of objective response will be right-censored for subjects who achieve CR or PR and meet 1 of the following conditions: 1) non-protocol anticancer treatment started before documentation of disease progression, 2) death or documented disease progression after more than 1 missed disease assessment visit, or 3) alive and does not have documentation of disease progression before a data analysis cutoff date.

The duration of objective response will be summarized descriptively using the Kaplan-Meier method. The 50th percentile of the Kaplan-Meier distribution will be used to estimate the median response duration.

Progression-free survival (PFS) will be measured as from the date of enrollment to the date of documented progression or death (whatever the cause). Subjects who are alive and progression free at last follow-up (up to a year from first treatment at Cycle 1 day 1) will be censored. Those who start another anticancer treatment without evidence of progression will be censored at start date of the new therapy.

The PFS will be summarized descriptively using the Kaplan-Meier method. The 50th percentile of the Kaplan-Meier distribution will be used to estimate the median PFS of each cohort of subjects.

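### Neither PFS censoring rule in Section 14.9 is tied to a tumour assessment, so unscanned time can count as progression-free for subjects who miss scans but are known to be alive

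*Combined protocol and SAP*

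**What the plan says.** Section 14.9 runs PFS from enrolment to documented progression or death from any cause. It has two censoring rules:

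- **Event-free subjects:** "Subjects who are alive and progression free at last follow-up" are censored, with a limit of one year from first treatment on Cycle 1 Day 1. The sentence says who is censored and sets a one-year limit. It does not name the censoring date, and *last follow-up* is not defined.
- **Subjects who switch therapy:** "Those who start another anticancer treatment without evidence of progression will be censored at start date of the new therapy". Here the date is named, and it is not a scan date.

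Section 6.5.3 describes two kinds of follow-up after treatment. Subjects who stop for reasons other than progression have disease assessments at least every 12 weeks until progression, new therapy, or one year from the last enrolled subject's first treatment. Separately, "Long-term follow-up survival information will be obtained in all surviving subjects who permanently discontinue study therapy", at intervals of about 3 to 6 months through 3 years, at clinic visits, through other site contact, "or via telephone or e-mail with the subjects/caregivers or referring physician offices". Section 6.12 likewise keeps subjects on study "for further collection of long-term information regarding survival". In Table 8 both kinds sit in one long-term follow-up row with one footnote (X).

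Section 14.3.1 puts every subject given at least one dose into the time-to-event analyses.

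**The concern.** Appendix 2 (Section 1.2) makes imaging the primary basis for assessing lymphoma, so progression is seen essentially only when a scan is done. If the censoring date can be a contact without a scan, the subject stays in the risk set over a period in which no progression could have been recorded, and the Kaplan-Meier curve is pushed upward.

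Missed scans are foreseeable. Appendix 2 (Sections 1.3 and 2.3) words post-treatment tumour follow-up as something investigators should ideally or optimally do, which is softer than Section 6.5.3. The study is single-arm, so no comparator carries the same bias. Expansion cohorts have 6 to about 20 evaluable subjects, so one subject is 1/6 = 17 to 1/20 = 5 percentage points of a cohort.

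**Working it through.** The plan states no PFS median, event count or precision, so there is no figure of its own to reproduce. The check is arithmetic on the schedule, followed by an illustration.

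**1. Unscanned time inside the one-year cap.** Table 8 footnote K places scans at Day 1 of Cycles 3, 5 and 7 (weeks 8, 16 and 24 with 28-day cycles), then every 3 months (about weeks 36 and 48). For a subject known alive at week 52:

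- on schedule, last scan at week 48: 52 − 48 = 4 weeks
- last scan at week 24: 52 − 24 = 28 weeks
- last scan at week 8: 52 − 8 = 44 weeks

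**2. Effect on 12-month PFS.** None of these assumptions is in the documents: exponential PFS with true median m of 9 or 6 months; scans at months 2, 4, 6, 9 and 12; a fraction f stops scanning at a time uniform over months 0 to 9, unrelated to progression; all who stop can be contacted to month 12; no deaths and no new therapy.

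S(t) = 2^(−t/m). Under last-contact censoring nobody is censored before month 12, so the estimate is the share with no detected progression:

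reported PFS(12) = (1 − f)·S(12) + f·D, with D = (2/9)·[1 + S(2) + S(4)] + (3/9)·S(6)

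D is the share of stoppers with no progression detected by their last scan. The term 1 is for those who stop before month 2 and have no on-study scan.

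- m = 9: S(2) = 0.857, S(4) = 0.735, S(6) = 0.630, S(12) = 0.397, so D = 0.576 + 0.210 = 0.786
- m = 6: S(2) = 0.794, S(4) = 0.630, S(6) = 0.500, S(12) = 0.250, so D = 0.539 + 0.167 = 0.705

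| Stop scanning | m = 9 (true 39.7%) | m = 6 (true 25.0%) |
|---|---|---|
| 10% | 43.6% | 29.6% |
| 20% | 47.5% | 34.1% |
| 30% | 51.4% | 38.7% |

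Censoring at the last scan recovers 39.7% and 25.0%. Each Kaplan-Meier step is then S(t) at the current scan divided by S(t) at the previous scan, among subjects actually scanned, and the product is S(12).

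**3. Cross-check on the protocol's weekly schedule.** Simulation of 200,000 subjects per scenario, scans at weeks 8, 16, 24, 36 and 48, stopping after week 8, 16 or 24, contact to week 52. The columns give 48-week PFS.

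| True median | Last-scan rule | Last contact, 10% stop | 20% | 30% |
|---|---|---|---|---|
| 26 weeks | 28% | 32% | 36% | 39% |
| 39 weeks | 43% | 46% | 49% | 53% |
| 52 weeks | 53% | 56% | 58% | 61% |

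The bias is about 3 to 4 points per 10% who stop scans. With nobody stopping, the two rules agree. The estimated median is the same under both rules (36 weeks, 48 weeks, not reached), except with a true median of 39 weeks and 30% stopping, where it moves from 48 weeks to not reached.

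**The case against.** Several objections stand and limit the point.

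- **The date is unstated.** Section 14.9 gives a status at last follow-up, and nothing says a survival call sets the PFS date. *Last follow-up* could mean disease follow-up. A reader might infer that the plan prescribes censoring at the last telephone contact; it does not. Last follow-up is the natural reading of the date, and survival contact is simply not excluded.
- **The one-year limit matters.** A reader might infer that three years of telephone contact count as progression-free. The limit in the same sentence rules that out.
- **Stopping treatment does not stop scans.** They stay due at least every 12 weeks, and their study-level end date (one year from the last enrolled subject's first treatment) cannot precede a subject's own one-year limit. Only subjects who miss required scans are affected.
- **Duration of response is not a useful contrast.** Its rule on "death or documented disease progression after more than 1 missed disease assessment visit" concerns events after a gap. The problem here is a subject with no event, and the rule for event-free responders names no scan date either.
- **The illustration is a worst case.** Survival contact is at the sponsor's discretion, some subjects withdraw consent to follow-up, and some switch therapy.

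Section 14.2 also defers detail to a SAP, which was not in the text available here and may settle the date. What remains is that the protocol wording permits unscanned time to count, and for switchers it says so outright, because the gap from last scan to new therapy is credited.

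**Conclusion.** The point holds as a gap in the PFS censoring rules. For subjects who miss scans but are known alive, up to about 44 weeks without imaging can be counted as progression-free within the one-year limit; those who keep to the schedule have about 4. If 10% to 30% of subjects did this, 12-month PFS would read roughly 4 to 14 points high under the assumptions above.

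That size rests on assumed medians and stopping rates, on every stopper being contactable, on stopping being unrelated to progression, and on the one-year limit running from the subject's own first treatment.

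A reader might infer that the trial's conclusions are at risk. The documents do not support that: PFS is not among the endpoints in Sections 5.4 to 5.6, it is summarised descriptively, the follicular lymphoma accrual boundaries use response rate, and the planned summary statistic, the median, mostly does not move. This is a cheap improvement.

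**What to change.** Replace the two PFS censoring sentences in Section 14.9, and carry the wording into the SAP:

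> Subjects alive without documented progression, including those who start new anticancer therapy without progression, are censored at the date of the last adequate tumour assessment on or before the cutoff or new therapy (Day 1 if none); survival-only contacts do not extend PFS.

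The cost is one sentence and no new data collection. The downside is that reported PFS becomes slightly less favourable.

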4.1.4.2. Efficacy

In Study LAM-002A-NHL-CLN01, efficacy has been assessed in subjects with NHL. Decreases in tumor metabolic activity were noted in 3 subjects with relapsed DLBCL receiving LAM-002A monotherapy but these changes did not meet formal criteria for objective response. Nine subjects with FL treated with LAM-002A monotherapy, LAM-002A in combination with rituximab, or LAM-002A in combination with atezolizumab have had substantial tumor regressions compromising 2 complete responses (CRs) and 7 partial responses (PRs). The responses have been long-lasting, with durations exceeding 12 months among several subjects with mature data. One subject with MZL receiving LAM-002A/rituximab also experienced a durable PR.

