6.1.3. Extension Stage (Stage 3)

The extension stage (Stage 3) can begin once the last study subject has completed at least 8 cycles of study treatment. At this time, the study sponsor will conclude the dose-escalation and expansion stages of the study, will collate and verify all study data through an appropriate data cutoff date, and will lock the study database for preparation of a study report. Subjects who are still safely benefiting from Stage 1 or Stage 2 study therapy as of the data cutoff date may electively continue their current regimen of study therapy in Stage 3, receiving clinical care and diagnostic testing consistent with conventional practice standards as deemed appropriate by the treating investigator. Therapy in Stage 3 may continue in the absence of protocol-defined reasons to discontinue therapy. During Stage 3, collection of clinical data by the sponsor will be limited to serious adverse event (SAE) reports. Study drug accountability will be managed per site procedures; relevant pharmacy records may be collected by the sponsor to document study drug disposition.

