- F All hematology and chemistry laboratory parameters should be assessed at Screening and at C1D1, C1D8, C1D15, C≥2D1 (all subsequent cycles), and then at least once prior to the start of all subsequent cycles and at EOT. Obtaining a chemistry laboratory parameter on Days 2 and Day 3 of Cycle 1 is only required in subjects with intermediate or high risk of TLS (per the risk definition in Section 6.8.1). Except for Days 1, 2, and 3 of Cycle 1, these parameters may be obtained within 72 hours prior to the planned day of collection. Abnormal test values should be monitored per protocol guidance.
- G Chemistry includes albumin, alkaline phosphatase, total bilirubin, BUN, calcium, carbon dioxide, chloride, creatinine, glucose, inorganic phosphorus, potassium, total protein, LDH, ALT, AST, sodium, and uric acid.
- H Urinalysis includes appearance, specific gravity and pH as well as a semi-quantitative "dipstick" evaluation of glucose, protein, bilirubin, ketones, leukocytes, and blood. Microscopic examination of sediment will be performed if urinalysis is positive for WBC, proteins or blood. Urinalysis may be obtained within 72 hours prior to the planned day of collection.
- I Pregnancy testing (serum or urine) will be required for women of childbearing potential (WCBP) only. Testing is required at Screening; within 72 hours of Day 1 of each cycle and at EOT. Test does not need to be repeated on C1D1 if baseline was negative and conducted within 72 hours of first dose.
- J Imaging as appropriate for disease indication will be conducted within 30 days of the first dose of study treatment. Suitable scans performed prior to screening and within 30 days before first dose may be used for baseline tumor assessments.
- K Assessment of disease status will be conducted with standard clinical measurements: PE, CBCs, bone marrow aspirates/biopsies, and imaging as appropriate for indication. During treatment, scans will be repeated for tumor assessment within 7 days of Day 1, Cycles 3, 5, and 7 then every 3 months until PD or use of alternative antineoplastic therapy. For subjects still in response after 1 year, intervals for radiographic surveillance may be every 6 months. Subjects with CLL who achieve CR will require assessment of MRD by flow cytometry of bone marrow and peripheral blood.
- L Imaging at EOT is not required if PD has already been radiographically documented or last imaging was within 30 days of EOT visit.

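### Section 14.9 ends PFS follow-up one year after first treatment, against the longer follow-up stated elsewhere; read literally, no median PFS above about 12 months can be reported

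*Combined protocol and SAP*

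**What the plan says.** Section 14.9 starts the PFS clock at enrollment and counts documented progression or death from any cause. Its censoring rule is: "Subjects who are alive and progression free at last follow-up (up to a year from first treatment at Cycle 1 day 1) will be censored". The planned output is a median for every cohort: "The 50th percentile of the Kaplan-Meier distribution will be used to estimate the median PFS of each cohort of subjects".

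Other parts of the protocol set a different horizon:

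- **Disease follow-up after stopping treatment without progression.** Section 6.5.3 continues it "for up to 1 year from the last enrolled subject's first treatment (Cycle 1 Day 1) whichever comes first", the other stopping points being progression and new anticancer therapy. The synopsis, section 6.11 and the long-term follow-up footnotes to Tables 8 to 11 say the same.
- **Scans on treatment.** All four schedules in section 8.7 repeat imaging until progression or another antineoplastic therapy. The two monotherapy schedules (Tables 8 and 9) provide expressly for later scans: "For subjects still in response after 1 year, intervals for radiographic surveillance may be every 6 months".
- **Duration of response (DOR).** Section 14.9 censors subjects who are alive without documented progression by reference to a data analysis cutoff date. It sets no one-year limit.

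**The concern.** Only 14.9 counts the year from first treatment without mentioning the last enrolled subject. A programmer who follows it as written would stop each subject's PFS at about month 12, while the trial goes on collecting progression data on earlier-enrolled subjects and on anyone still on treatment.

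Two endpoints that share a progression date could then disagree. Suppose a subject responds at week 8 and progresses at month 20. DOR is about 18 months, but PFS is censored at about 12 months if the limit is applied to that progression.

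What is at stake is the planned median PFS per cohort. It would have a ceiling set by the censoring rule, and a reader of the study report would not see that from the estimate alone.

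**Working it through.** **Figure to reproduce.** There is none. The documents give no expected median PFS, PFS event count or PFS power. The check is therefore of what the rule implies.

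**Step 1: the ceiling.** If every progression-free subject is censored 12 months after Cycle 1 Day 1, the Kaplan-Meier curve cannot fall after that point. Any median it yields is at most 12 months, plus the interval from enrollment to Cycle 1 Day 1, because the PFS clock starts at enrollment. This needs no distributional assumption.

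**Step 2: chance that a median can be estimated.** Inputs are n = 20 (upper size of the two enlarged follicular lymphoma cohorts) and n = 6 (the other expansion cohorts), from Table 2 and section 14.1.2. Assumptions are exponential PFS, no censoring before month 12, and no enrollment-to-dosing gap.

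With no earlier censoring, the curve after d events is 1 − d/n. It reaches 0.5 only if d ≥ n/2, that is 10 of 20 or 3 of 6. With F(12) = 1 − 2^(−12/median), the probability is P(X ≥ n/2), where X is binomial(n, F(12)).

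| True median (months) | F(12) | n = 20 | n = 6 |
|---|---|---|---|
| 9 | 0.603 | 0.879 | 0.825 |
| 12 | 0.500 | 0.588 | 0.656 |
| 15 | 0.426 | 0.325 | 0.509 |
| 18 | 0.370 | 0.165 | 0.394 |
| 24 | 0.293 | 0.041 | 0.243 |

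In simulation (4,000 trials per setting) no estimate under the cap exceeded 12.0 months. When the true median is longer, every estimate obtained is therefore too low, and otherwise the median is not reached.

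**Step 3: effect of the scan schedule.** With scans at weeks 8, 16, 24, 36, 48 and 60, as in the rituximab schedule and approximately in the monotherapy schedules, the last scan inside the year is week 48. For progression found by scan, the ceiling becomes 48 × 7 / 30.4375 = 11.0 months. For n = 20 the simulated chance of an estimable median falls to 0.49, 0.25 and 0.11 for true medians of 12, 15 and 18 months.

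**Step 4: with the section 6.5.3 horizon instead.** Each subject's follow-up is 12 months plus a uniform share of the accrual period. The documents do not give an accrual span, so 12, 24 and 36 months were assumed. Simulated probabilities for n = 20:

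| True median (months) | 12-month accrual | 24-month accrual | 36-month accrual |
|---|---|---|---|
| 15 | 0.85 | 0.98 | 1.00 |
| 18 | 0.70 | 0.93 | 0.98 |
| 24 | 0.43 | 0.74 | 0.92 |

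For n = 6 and a true median of 18 months the values are 0.67, 0.83 and 0.91. These figures suppose that the cutoff falls a full year after the last subject's first dose. An earlier cutoff would give a smaller gain.

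**The case against.** The strongest reply is that the sentence sets no individual cap. It does not say each subject's own first treatment. The same horizon appears throughout the protocol with the last enrolled subject named, so the parenthesis may be that phrase shortened. This may well be the intent, and it is why the point is a conflict to reconcile rather than an established individual limit. It does not remove the point, because the sentence as written would be programmed differently from 6.5.3.

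Second, a reader might infer that progression recorded after month 12 is discarded. The text does not say so. The event definition has no time limit, and the censoring sentence covers only subjects who are alive and progression free at last follow-up. Exclusion of later events is the natural consequence of a one-year limit, but it is an inference.

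Third, a reader might conclude that median PFS in follicular lymphoma would be not reached by construction. The documents do not support that. Section 4.1.4.2 does say: "The responses have been long-lasting, with durations exceeding 12 months among several subjects with mature data". But that is duration among responders, pooled over three regimens, and not PFS in a cohort. With a target response rate of about 40% on monotherapy, non-responders could determine the median. Even at a true median of 12 months, a cohort of 20 yields an estimate more often than not.

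Fourth, a reader might extend the point to Stage 3, which section 6.1.3 allows once the last subject has completed 8 cycles (8 × 28 = 224 days, or 32 weeks): "During Stage 3, collection of clinical data by the sponsor will be limited to serious adverse event (SAE) reports". That is a separate design choice. Data are locked at a cutoff first, and censoring at a cutoff is ordinary. At most 4 subjects are expected to move over (section 6.2), and section 16 ends routine monitoring by then. Collecting progression dates after lock is not part of this point.

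Finally, PFS is not among the endpoints in sections 5.4 to 5.6, and section 14.2 lets the SAP modify the protocol's analysis plans. Both facts limit the consequence. The SAP's own censoring rule should be checked before the text is changed.

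**Conclusion.** The conflict holds on the wording of 14.9. Taken literally, the rule puts a ceiling of about 12 months on any reportable median PFS, and that ceiling rests on no distributional assumption. The probabilities in the working do: they assume exponential PFS, no earlier censoring and medians chosen as scenarios, since the plan states none. The ceiling matters when a cohort's true median is near or above 12 months. For a true median well below that, the curve that determines the estimate is essentially unchanged.

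The consequence is limited to a descriptive summary. The expansion-stage stopping boundaries use response rates and adverse-event discontinuations, so no sample size, boundary or error rate is affected. The claims of discarded data, of a median never reached in follicular lymphoma, and of a Stage 3 defect go further than the documents allow.

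**What to change.** In section 14.9, delete the parenthesis that limits follow-up to a year. State that subjects alive and progression free are censored at their last adequate tumour assessment on or before the data analysis cutoff date. That matches the cutoff already used for DOR and the horizon in section 6.5.3. The existing rule for subjects who start another anticancer treatment can stay. If the SAP repeats the one-year wording, change it there too.

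The cost is one sentence. It needs no extra scans, visits or data fields, because the assessments are already scheduled, and it changes neither treatment nor sample size.
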